APPENDIX A: CLINICAL EVENTS TO BE RECORDED IN ECRF

Cardiac events within 30 days

- All-cause mortality
- Cardiac mortality
- Cardiogenic shock
- Congestive heart failure
- Recurrent myocardial infarction
- Stent thrombosis
- Rehospitalisation for cardiac reasons
- Rehospitalisation for non-cardiac reasons

Safety events with 30 days

Total stroke, intracranial haemorrhage, ischaemic stroke, haemorrhagic conversion within 30 days

- Procedure related major bleeds (within 48 hours)
- Non-intracranial bleeds (major, minor) and need for blood transfusions up to 30 days

Evaluations at 1 year

- All-cause mortality

APPENDIX B: DEFINITIONS OF CLINICAL EVENTS

B1. BLEEDS

Major bleeds

Severe bleed: a bleed that leads to haemodynamic compromise requiring intervention (e.g. blood or fluid replacement, inotropic support, surgical repair) or life-threatening or fatal bleeds.

Moderate bleed: bleeding requiring transfusion of blood but which does not lead to haemodynamic compromise requiring intervention.

Minor bleeds

Bleeding neither requiring blood transfusion nor leading to haemodynamic compromise.

PS Intracranial bleeds will be reported separately

B2. MAJOR CARDIAC EVENTS

Congestive heart failure

A positive diagnosis consists of at least one of the following conditions requiring treatment with diuretics:

- Pulmonary oedema/congestion on chest x-ray without suspicion of a non-cardiac cause;
- Rales >1/3 up from the lung base (Killip class 2 or higher);
- Pulmonary capillary wedge pressure (PCWP) >25 mmHg;
- Dyspnea with $pO_2 < 80$ mmHg or O_2 sat < 90 % (no supplemental O_2) in the absence of known lung disease

Killip class

I: The absence of rales over the lung fields and the absence of an S3.

II: The presence of rales that do not clear with coughing, over one half or less of the lung fields or the presence of an S3.

III: The presence of rales that do not clear with coughing, over more than half of the lung fields.

IV: Cardiogenic shock.

Cardiogenic shock

Defined as one of the following:

1. Systolic blood pressure < 90 mmHg for at least 30 min (or the need for supportive measures to maintain a systolic blood pressure of > 90 mmHg) in the presence of a heart rate of > 60 beats/min

in association with signs of end organ hypoperfusion (cold extremities, low urinary output < 30 ml/h and/or mental confusion);

2. A cardiac index < 2.2 l/min/m² in the presence of a pulmonary capillary wedge pressure (PCWP) of >15 mmHg.

Reinfarction

Reinfarction in the absence of a coronary intervention and within 18 hours after randomization:

Recurrent signs and symptoms of ischaemia at rest, accompanied by new or recurrent ST-segment elevations of ≥ 0.1 mV in at least two contiguous leads lasting ≥ 30 min.

Reinfarction related to PCI

≤ 48 h after the index procedure:

Coronary intervention related myocardial infarction is arbitrarily defined by elevation of cardiac troponin values >5 multiplying 99th percentile URL in patients with normal baseline values (≤ 99 th percentile URL) or a rise of cardiac troponin values $>20\%$ if the baseline values are elevated and are stable or falling. In addition, either symptoms suggestive of myocardial ischemia or new ischemic ECG changes or angiographic findings consistent with a procedural complication or imaging demonstration of new loss of viable myocardium or new regional wall motion abnormality are required.

>48 h after the index procedure:

Detection of a rise and/or fall of cardiac troponin values with at least one value above the 99th percentile URL and with at least one of the following:

- Symptoms of ischemia;
- New or presumed new significant ST-T changes or new left bundle branch block;
- Development of pathological Q waves in the ECG;
- Imaging evidence of new loss of viable myocardium or new regional wall motion abnormality;
- Identification of an intracoronary thrombus eg stent thrombosis by angiography or autopsy

Reinfarction related to cardiac surgery

≤ 48 h after the index procedure:

Cardiac and non-cardiac surgeries related myocardial infarction are arbitrarily defined by elevation of cardiac troponin values >10 multiplying 99th percentile URL in patients with normal baseline values (≤ 99 th percentile URL) or a rise of cardiac troponin values $>20\%$ if the baseline values are elevated and are stable or falling plus either new pathological Q waves or new left bundle block or angiographic documented new graft or new native coronary artery occlusion or imaging evidence of new loss of viable myocardium or new regional wall motion abnormality.

>48 h after the index procedure:

Detection of a rise and/or fall of cardiac troponin values with at least one value above the 99th percentile URL and with at least one of the following:

- Symptoms of ischemia;
- New or presumed new significant ST-T changes or new left bundle branch;
- Development of pathological Q waves in the ECG;
- Imaging evidence of new loss of viable myocardium or new regional wall motion abnormality;
- Identification of an intracoronary thrombus by angiography or autopsy

Aborted myocardial infarction

Aborted myocardial infarction⁵⁴ will be assessed by means of ECG as ST-segment resolution relative to baseline value and cardiac marker enzymes as done previously in STREAM-1⁵⁵. Peak levels of troponin I/T (CK/CK-MB) will be collected at baseline, and 8-12 hrs and 24 hrs after randomisation. Quantification of aborted myocardial infarction will be defined as troponin values \leq 5 times the upper limit of normal (ULN) within 24 hours of randomisation (or CK/CK-MB levels \leq 2 times ULN). Only peak values of markers of necrosis (expressed as times exceeding the upper limit of normal) will be recorded in the eCRF; the complete set of measured values will however be kept in the source documents.

Rescue PCI post PPI therapy

If ST-segment resolution is $<50\%$ relative to the ST-segment elevation in the qualifying lead at baseline, irrespective of the presence or absence or clinical symptoms

Refractory ischaemia

Symptoms of ischaemia with ST-deviation or definite T-wave inversion persisting for at least 10 min despite medical management while in-hospital and not fulfilling the diagnosis of infarction.

Major arrhythmias

Sustained ventricular tachycardia (ventricular tachycardia lasting ≥ 30 seconds or requiring cardioversion or causing symptoms/hypotension), ventricular fibrillation, asystole, atrial fibrillation, 2nd and 3rd degree atrio-ventricular block.

Invasive procedures

Include CABG, PTCA, stent placement, intra-aortic balloon.

Other major cardiac events

Other major cardiac events include sustained hypotension, acute mitral regurgitation, acute ventricular septum defect, pericarditis, pulmonary embolism and tamponade.

Sustained hypotension

SBP < 90 mmHg for > 30 minutes

Rehospitalisation for cardiac reasons

If, after discharge, a patient is readmitted to the hospital until day 30 due to cardiac reasons, this information must be recorded in the eCRF. Any event requiring unscheduled readmission will be considered a serious adverse event (SAE) and recorded as described in section 5.2.1. Only if readmission was scheduled, e.g. because of a routine or planned procedure, will the event leading to rehospitalisation not be considered as a serious adverse event.

Rehospitalisation for non-cardiac reasons

Data about any rehospitalisation for non-cardiac reasons occurring after discharge from initial hospitalisation until day 30 will be collected in the eCRF and have to be recorded on SAE reports in accordance with section 5.2.1. Only if rehospitalisation was scheduled, e.g. because of a routine or planned procedure, will it not be considered as a serious adverse event.

Statistical analysis of clinical events

The analysis will be described in detail in the statistical analysis plan. Clinical events of interest will be assessed as single or composite endpoints for evaluation. All statistical tests on clinical events are of exploratory nature based on descriptive statistics for formal statistical hypotheses generation. For comparison the same composite clinical event rates as in STREAM-1 will be analysed (see APPENDICES). The primary comparisons will be based on the differences between Group PhI and PPCI. Differences between groups and their 95% CI will be calculated. Should a statically significant difference appear in at least one clinical endpoint, i.e. the corresponding CI excludes 0 (no difference), and if there is also consistency for the other endpoints, then this will be considered evidence for a clinically meaningful difference between treatments which should be confirmed in a later study. Should no statistically significant difference be apparent, the CI will be examined to determine to what level a worse outcome can be excluded as has been done with the primary endpoint in STREAM-1.

A formal interim analysis will be performed after 50 % of the planned recruitment. The aim of this analysis is to evaluate the usefulness and feasibility of enlarging the study based on the results.

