Troponin I/T (or CK, CK-MB) will be measured at baseline, i.e. pre-hospital or on arrival at ER of the community hospital, as well as 8-12 hrs and 24 hrs after randomisation. If symptoms suggest occurrence of recurrent myocardial ischaemia or reinfarction during in-hospital stay, marker levels should be determined to confirm the diagnosis. Individual values will not be recorded in the eCRF, for the qualifying myocardial infarction only peak values expressed as times exceeding upper limit of normal will be recorded (cf. also section 5.1.2).

- 12-lead ECG:

For ECG measurements please refer to section 5.1.2.

- TIMI flow grade:

TIMI flow grade of the infarct-related artery (IRA) will be assessed by standard angiographic measurement during routine catheterisation in Phi Group or, for the PPCI Group, before PCI (first contrast injection) and after PCI (last contrast injection) as measured by the local investigator.

- Killip class:

Killip class will be determined before randomisation to check for patient eligibility. In case the ambulance staff consists of paramedics only, the responsible PI (or sub-investigator) must make sure the staff is sufficiently trained to perform the Killip classification. In the exceptional case that the Killip classification cannot be done at randomisation, it will be done upon arrival at the hospital.

- Adverse events:

Expected adverse events (AEs) related to tenecteplase are listed in the current version of the Tenecteplase Investigator Brochure⁵⁰, filed in the Investigator Site File.

Adverse events will be recorded according to the following procedure until day 30 (cf. Figure 2):

All adverse events (serious and non-serious) need to be reported in the eCRF.

In addition an SAE form must be completed and submitted within 24 hours for any SERIOUS adverse event:

- related to study treatment (Tenecteplase, Clopidogrel, catheterisation/PCI)
- not related to study treatment AND not on the list of the STEMI related events

ADVERSE EVENT REPORTING

[figure not shown]

Figure 5: Adverse Event Reporting

During screening/baseline, the patient's condition is assessed; any relevant changes from

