Baseline	Pre-PCI hospital: on site/ambulance/ER community hospital	ECG for assessment of STEMI entry criteria
90 min after bolus tenecteplase or earlier if indicated	In-PCI hospital: emergency dept. or CCU	Assessment of reperfusion
In case of catheterisation (with or without PCI/stenting) or rescue or urgent PCI, respectively: - immediately before - and 30 min after the end of the procedure.	In-PCI hospital: catheter laboratory	Re-assessment of reperfusion

Timing of ECG	Location	Reason for ECG
Any time, if indicated (serial ECGs)	In-PCI hospital	Verification of ischaemia or reinfarction
At 4 days or hospital discharge whichever comes first	In-PCI hospital	Assessment infarct size using QRS score

Collection of data

During the patient's stay in hospital (i.e., until and including the day of discharge) the following data will be collected:

- Concomitant therapy
- Troponin I/T (CK/CK-MB) 8-12 hrs and 24 hrs after randomisation, respectively, and also at any time in case of signs and symptoms suggestive of recurrent myocardial ischaemia or reinfarction
- 12-lead ECG (please refer to Table 4)
- Data on catheterisation/coronary intervention(s)
- TIMI flow grade (before PCI and at the end of the angiographic procedure)
- Any occurrence of adverse events, and serious adverse events/serious clinical events

The following assessments will be performed on the **day of discharge from hospital** (or transfer to a rehabilitation centre or nursing home)

- Blood test for haematology as per hospital routine
- 12-lead ECG (cf. Table 4)
- Any occurrence of adverse events, and serious adverse events/serious clinical events

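### The post-PCI and post-surgery reinfarction rules accept only troponin, although the protocol lets sites measure CK/CK-MB instead, so a CK-only patient cannot meet the written definition.

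*Protocol*

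**What the plan says.** Protocol Appendix B2 defines reinfarction by setting and time.

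- After PCI, up to 48 hours: "Coronary intervention related myocardial infarction is arbitrarily defined by elevation of cardiac troponin values", plus clinical, ECG, angiographic or imaging evidence.
- After surgery, up to 48 hours: "Cardiac and non-cardiac surgeries related myocardial infarction are arbitrarily defined by elevation of cardiac troponin values", plus ECG, angiographic or imaging evidence.
- Beyond 48 hours, worded alike for PCI and surgery: "Detection of a rise and/or fall of cardiac troponin values with at least one value above the 99th percentile URL", plus one supporting finding.
- The only rule that needs no marker is headed "Reinfarction in the absence of a coronary intervention and within 18 hours after randomization". It rests on symptoms and ST elevation.

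The measurement sections are wider. Section 5.2.1 says "Troponin I/T (or CK, CK-MB) will be measured at baseline" and gives the later time points. For a suspected reinfarction it says only that "marker levels should be determined to confirm the diagnosis", without naming a marker. Section 6.2.2.1 lists "Troponin I/T (CK/CK-MB) 8-12 hrs and 24 hrs after randomisation, respectively, and also at any time in case of signs and symptoms" of recurrence, and section 6.2.2.2 applies the same in-hospital assessments to the PPCI group. For aborted infarction, Appendix B2 does give both routes: the troponin limit applies "within 24 hours of randomisation (or CK/CK-MB levels" at a limit of their own. SAP Table 8.1 has separate blocks for troponin, CK-MB and CK.

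Reinfarction is a component of the clinical endpoint of primary interest (SAP 6.1.1) and a secondary endpoint (SAP 6.2). The SAP gives no definition of its own.

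**The concern.** The marker schedule and the event definition do not fit together. Take a patient at a site that uses CK-MB. On day 3 after PCI there is chest pain with new ST elevation, CK-MB rises again, and angiography shows an occluded stent. The site has followed the protocol, but the event fails the written rule because no troponin value exists.

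At stake is the count of one component of the composite, which also feeds the cumulative incidence curves (SAP 8.12) and the weighted composite (SAP 10). The closing part of Protocol Appendix B treats a confidence interval that excludes zero for one clinical endpoint, with consistency in the others, as evidence of a difference. Failing that, it uses the interval to say how much worse an outcome can be excluded. Both readings assume that events are counted by one workable definition.

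**Working it through.** **1. Rules against permitted markers**

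| Rule (Appendix B2) | Troponin required | CK/CK-MB route |
|---|---|---|
| PCI, up to 48 h | yes; judged against a baseline troponin | none |
| PCI, beyond 48 h | yes | none |
| Surgery, up to 48 h | yes; judged against a baseline troponin | none |
| Surgery, beyond 48 h | yes | none |
| No intervention, within 18 h | no marker | not needed |
| No intervention, after 18 h | no rule at all | – |
| Aborted infarction | up to 5 × ULN | up to 2 × ULN |

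Sections 5.2.1 and 6.2.2.1 and footnote d of the Flow Chart allow or imply CK/CK-MB at baseline, at 8-12 h, at 24 h and when recurrence is suspected. So four of the five reinfarction rules cannot be met by a CK-only patient.

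**2. Plan figures**

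The plan states no figure for this point, so there is none to reproduce. Protocol 7.5 gives 400 and 200 patients (600 split 2:1) and a reference composite rate of 18-20% in patients aged 60 or over. I use 19% in both arms. With the log method,

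SE(log RR) = √[0.81/(400 × 0.19) + 0.81/(200 × 0.19)] = √(0.01066 + 0.02132) = 0.179,

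so a true RR of 1.00 has a 95% CI of exp(±1.96 × 0.179), about 0.70 to 1.42.

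**3. Possible shift in the composite**

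None of these inputs is in the documents; all are assumed:
- m, the rate of reinfarction as a patient's only composite event: 1-4%.
- c, the share of patients with CK/CK-MB only: 5-30%, equal in both arms because randomisation is stratified by centre.
- s, the share of reinfarctions that fall under the troponin-only rules: 0.5-1.0 in PhI, 0.9-1.0 in PPCI.

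Observed rate per arm = 0.19 − m × c × s.

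- Upper end (m = 0.04, c = 0.30, s = 0.5 in PhI and 1.0 in PPCI): 0.184/0.178 = 1.034.
- Lower end (same m and c, s = 1.0 in PhI and 0.9 in PPCI): 0.1780/0.1792 = 0.993.
- Expected events lost: 0.1 to 4.8 of 400 in PhI (400 × 0.01 × 0.05 × 0.5; 400 × 0.04 × 0.30 × 1.0) and 0.1 to 2.4 of 200 in PPCI (200 × 0.01 × 0.05 × 0.9; 200 × 0.04 × 0.30 × 1.0).

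**4. Reinfarction alone**

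Observed RR for a true RR of 1 = (1 − c × s in PhI)/(1 − c × s in PPCI). At c = 0.30 the extremes are 0.85/0.70 = 1.21 and 0.70/0.73 = 0.96. Equal shares give 1.00.

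**5. Does the direction follow?**

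Let q be the share of PhI reinfarctions caught by the marker-free rule, and g the share in the gap after 18 h without intervention, which is lost whatever marker is used. Place all PPCI reinfarctions under the troponin rules.

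PhI keeps 1 − g − c(1 − q − g); PPCI keeps 1 − c. The ratio falls below 1 once g > cq/(1 − c).

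At c = 0.10:
- q = 0.20: the ratio is 0.92/0.90 = 1.02 with no gap, and falls below 1 once g exceeds 0.02/0.90 = 2.2%.
- q = 0.60: the ratio is 0.96/0.90 = 1.07 with no gap, and falls below 1 once g exceeds 0.06/0.90 = 6.7%.

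The documents give none of c, q or g, so the sign is open.

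**The case against.** The strongest reply is that nothing discards such an event automatically. Reinfarction is entered by the site in the eCRF (section 5.2.2), it is not among the centrally adjudicated items in section 5.5, and the SAP does not derive it from marker values. A CK site may also draw troponin when reinfarction is suspected, and two late values could satisfy the rule beyond 48 hours. A reader might infer that CK-only patients can never have a counted post-PCI reinfarction. The documents do not support that; what holds is that they cannot meet the definition as written. The reply does not remove the problem: an unblinded site must choose between the definition and its own judgement, and a late troponin does not supply the baseline value against which the rules up to 48 hours are judged.

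A reader might also infer that the loss falls hardest on PPCI. There is a mechanism for it. All PPCI patients are expected to have PCI, while PhI patients on the planned route wait at least 6 hours and can still meet the marker-free rule until 18 hours. But section 5.3.3 expects rescue in 25 to 30% of PhI patients, who then move to the same troponin rules, and the gap after 18 hours affects PhI patients who are catheterised late or have no PCI. Centre stratification should balance CK-only use between arms, though not time spent under each rule.

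Finally, the trial is exploratory and has no primary hypothesis, and the plausible composite shift is small. That stands, and it limits how much weight the point can carry.

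**Conclusion.** The mismatch is confirmed from the text alone. It is an inconsistent stated rule for a component of the endpoint of primary interest, not just missing detail. Some undercounting of post-procedure reinfarction is possible. Neither its size nor its direction between arms is fixed by the documents, so a claim of bias against either strategy should not be made. Under the assumed inputs above, the composite RR would move by between −0.7% and +3.4%. The reinfarction RR alone could read 0.96 to 1.21, and its outer values need 30% CK-only patients, a share that nothing in the documents supports or excludes. These ranges cover the troponin wording only, not the gap after 18 hours. The reason to act is that the definition cannot be applied to data the protocol allows, not that a large distortion is expected.

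**What to change.** Reconcile the reinfarction definition with the permitted markers, in the SAP or the event definition:

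- Beyond 48 hours, after PCI or surgery: where troponin is absent, accept a rise and/or fall of CK-MB (or CK if CK-MB is also absent) with at least one value above that assay's upper limit, plus the supporting evidence already required.
- Up to 48 hours: state a separate CK/CK-MB criterion, set without knowledge of outcome by arm. Do not carry over the troponin multiples of 5 and 10; the aborted-infarction rule shows that the protocol itself uses different multiples by marker.
- Add a rule for reinfarction in patients without an intervention after 18 hours.
- Report by arm the number of CK-only patients and the number of reinfarctions classified by each marker.

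The text change is short. The work lies in the data: section 5.2.1 keeps individual marker values out of the eCRF and Appendix B2 leaves the full set in source documents, so suspected events need targeted site queries and not just programming. With about 600 patients this is modest. The drawback is that CK and CK-MB are less sensitive than troponin, so some small events would still be missed at CK sites.

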## **6 Endpoints**

### ***6.1 Efficacy endpoints of primary interest***

#### **6.1.1 Clinical endpoint**

The efficacy endpoint of primary interest is all cause death, shock ,CHF and reinfarction at day 30.

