### **8.5 Efficacy endpoints of primary interest**

#### **8.5.1 Clinical endpoint**

The primary efficacy endpoint will be analysed by presenting the event rates and the 95% confidence intervals (two-sided) separately for each treatment group. In addition, the two treatment groups will be compared using a working Poisson regression model (Zhou (2004)) from which the between-group comparison will be estimated by means of a relative risk with a 95% confidence interval (two-sided).

In case there are no events in a particular treatment group (before imputation), an artificial observation in each cell (treatment group by event) with weight 0.5 will be added in order to estimate the relative risk.

Furthermore, the risk difference with a 95% confidence interval will be calculated using PROC FREQ.

Standard multiple imputation methodology as described in Section 8.1 will be applied to combine the results over the different multiple imputations, if applicable.

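### Appendix B's two-part evidence rule has an unknown false-positive rate, and the unnamed risk-difference interval behind it can fire too easily for rare events such as ICH

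*Protocol*

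**What the plan says.** The last part of Protocol Appendix B, on the statistical analysis of clinical events, calls the tests exploratory and leaves the detail to the SAP. It then makes the between-arm difference the basis of comparison: "Differences between groups and their 95% CI will be calculated".

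A conditional rule follows.
- **Trigger:** "Should a statically significant difference appear in at least one clinical endpoint", meaning that the interval for that difference excludes 0.
- **Second condition:** "and if there is also consistency for the other endpoints".
- **Consequence:** "evidence for a clinically meaningful difference between treatments which should be confirmed in a later study".

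The SAP neither repeats nor refines this rule. It does name a lead clinical endpoint in 6.1.1: "The efficacy endpoint of primary interest is all cause death, shock ,CHF and reinfarction at day 30". On the interval itself, SAP 8.5.1 says only that "the risk difference with a 95% confidence interval will be calculated using PROC FREQ". The same section adds half-weight observations when an arm has no events, but for the stated purpose of estimating the relative risk.

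**The concern.** An exploratory trial need not control family-wise error. This plan goes a step further, however: it commits in advance to what a significant interval will be called. Three things leave the operating characteristics of that commitment open.

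- **Endpoint set.** The rule does not say which endpoints can trigger it.
- **Consistency.** No threshold or direction rule is given, and many endpoints are nested: death, death and shock, death and shock and CHF, and the full composite. A chance imbalance in one component therefore carries into several others.
- **Interval method.** The trigger depends on a risk-difference interval whose type is not stated. For rare events the choice of type can decide whether 0 is excluded.

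The third matters most for intracranial haemorrhage. Protocol 7.5 cites earlier ICH rates of 1.7% and 0% in this age group, so an arm with no events is foreseeable. An apparent ICH signal, or its absence, could then turn on a software default.

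**Working it through.** The documents give no false-positive rate, so there is no figure of the plan's own to reproduce.

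**1. How many endpoints.**
- Narrow reading, Protocol 5.1.2: death, shock, heart failure, recurrent MI, rescue PCI and aborted MI. Rescue PCI exists only in the pharmaco-invasive arm, which leaves 5; with the composite, 6.
- Wide reading, SAP 6.1.1 and 6.2 to 6.4: 1 + 10 + 12 + 2 = 25 by bullets, or 1 + 10 + 14 + 2 = 27 if major bleeds count as three.

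**2. Trigger alone, no true effect.** If the endpoints were independent, P(at least one interval excludes 0) = 1 - 0.95^k:

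| k | Probability |
|---|---|
| 6 | 26.5% |
| 25 | 72.3% |
| 27 | 75.0% |

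Independence overstates this. A simulation with 400 and 200 patients, 27 nested endpoints, equal rates in both arms and 3,000 runs per scenario gave 57 to 68%. Component rates were assumed, giving a composite rate of 12 to 27% against the 18 to 20% in Protocol 7.5. Latent correlation was 0 to 0.4, and both Wald and pooled-variance tests were tried.

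**3. Both parts of the rule, same simulation.**

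| Meaning given to consistency | Rule fires with no true effect |
|---|---|
| No significant result the other way | 49 to 59% |
| Also more than half in the same direction | 32 to 43% |
| At least 75% in the same direction | 5 to 14% |
| At least 90% in the same direction | 0.2 to 2% |
| None in the opposite direction | below 1% |

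**4. Interval method for a rare event.** Take ICH of 4/400 against 0/200, so d = 0.0100.
- Wald: SE = sqrt(0.01 × 0.99/400 + 0 × 1/200) = 0.004975. Limits are 0.0100 ± 1.96 × 0.004975, or 0.02 to 1.98 points. The empty arm adds nothing to the SE, as if its zero rate were known exactly.
- Newcombe: the Wilson limits are 0.0039 to 0.0254 for 4/400 and 0 to 0.0188 for 0/200. Lower limit = 0.0100 - sqrt((0.0100 - 0.0039)² + 0.0188²) = -0.98 points. Upper limit = 0.0100 + (0.0254 - 0.0100) = 2.54 points.
- Fisher's exact p = 0.31.

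**5. Exact type I error.** Enumerating all outcomes for 400 and 200 patients with equal true rates:

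| True rate | Wald | Newcombe |
|---|---|---|
| 0.5% | 5.6% | 1.7% |
| 1% | 8.8% | 3.1% |
| 1.7% | 6.3% | 3.9% |

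Most of the excess comes from the empty smaller arm. At 1%, P(0 of 200) = 0.99^200 = 0.134 and P(at least 4 of 400) = 0.568. Their product, 7.6%, is most of the 8.8%.

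**The case against.** **The rule has a second condition.** A reader who stops at the trigger might infer that any one significant interval is enough, and that the rule would therefore fire in most null trials. The text does not support that. Consistency is also required, and under a strict meaning the rate falls below 1%. This stands: the 57 to 75% figures describe only the trigger.

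**Twenty-seven is the high end of the count.** The protocol's own list of clinical events supports about 6. This also stands, which is why the range is given.

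**The trial is openly exploratory and points to a later study.** This stands as a limit on the harm. It does not settle what this trial's report may call evidence of a clinically meaningful difference, and no effect size is tied to that phrase.

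**Safety endpoints are analysed by relative risk.** SAP 8.7 says so, and mock Table 12.1 has no risk-difference column. With the half-weight correction, 4/400 against 0/200 gives (4.5/401)/(0.5/201) = 4.5, with 95% limits of about 0.24 to 83, plainly not significant. This stands in part. Section 8.7 refers back to 8.5.1, which includes the risk difference, and Appendix B judges significance by a difference excluding 0. The mock table does not decide the matter, because Table 10.1.1 also lacks a risk-difference column for the composite, where 8.5.1 requires one.

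**The SAP does not say Wald.** This is correct, and the interval results are conditional on it.

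**The rule is not the plan's only conclusion.** Appendix B goes on to say that, without a significant difference, the interval will be used to see how much worse an outcome can be excluded. A claim that the evidence rule is the sole formal conclusion would be wrong.

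**Conclusion.** The point holds in two parts.

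First, Appendix B attaches the phrase "this will be considered evidence for a clinically meaningful difference between treatments" to a rule whose false-positive rate cannot be known from the documents. The simulated range, below 1% to 59%, rests on assumed component rates and correlations and on the 27-endpoint reading. It shows how much depends on the undefined term; it is not an estimate of the rate this trial will have. That the rule would often fire is something a reader might infer, but the documents leave it open.

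Second, and more firmly, the interval that drives the trigger is unspecified, and the zero-event correction does not reach it. If Wald limits are used and the rule is applied to ICH, four events against none would meet the trigger although Fisher's p is 0.31. Type I error at a 1% rate would be 8.8% rather than the nominal 5%; the Newcombe limits give 3.1%. This part assumes the planned 400 and 200 patients and needs no assumption about correlation.

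The consequence is modest, since any finding is to be confirmed in a later study. The remedy is cheap.

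**What to change.** **SAP 8.5.1.** State that all risk-difference limits are score-type (Newcombe or Miettinen-Nurminen, named as a PROC FREQ option), including those for safety endpoints to which the Appendix B rule may be applied.

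**Evidence wording.** Replace it with a statement that a lone 95% interval excluding 0 is hypothesis-generating, to be read alongside the named 30-day composite and the ICH and major-bleeding results. Restricting the rule to the efficacy composite would be simpler, but would shut out bleeding, which Protocol 1.1 lists among the main objectives.

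**Cost.** One option and one or two sentences, with no change to data, sample size or conduct.
- Intervals widen for rare events: in the ICH example, from 1.98 - 0.02 = 1.96 points to 2.54 + 0.98 = 3.52 points. For common events little changes: at 72/400 against 40/200 (18% and 20%), Wald gives -8.7 to 4.7 points and Newcombe -9.0 to 4.4.
- If multiple imputation is triggered (more than 1% missing, SAP 5), score limits do not combine as an estimate and standard error, so the pooling step needs some extra work and its own sentence.
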